I will conduct the trial in accordance with the clinical investigation plan, Good Clinical Practice guidelines, ISO 14155:2011 (Clinical Investigation of Medical Devices for Human Subjects - Good Clinical Practice), as well as local regulations. I also accept respective revisions to the clinical investigation plan approved by authorized personnel of the Sponsor and by regulatory authorities.

Institution:

[name] [name]

Principal Investigator (Printed name)

Principal Investigator (Signature)

22/2/18

Date

PROTOCOL SUMMARY

TITLE	Clinical Evaluation of the Safety and Performance of Fractional RF for the Treatment of Surgical Scars Following Breast Augmentation, Abdominoplasty or Face Lift
SUMMARY	Split-body/face evaluator-blind study of the safety and performance of fractional RF for the treatment of surgical scars following breast augmentation, abdominoplasty or face lift. The study will enroll up to 50 female subjects requesting treatment of surgical scars following breast augmentation or abdominoplasty and up to 25 male and female subjects requesting treatment of surgical scars following face lift surgery. Subjects will receive a total of three treatments of their surgical scars at one-month intervals on one side of the body or facial incision only. Subjects will be followed up at one, two, three and ten months after their last treatment. Analysis will be performed on all subjects who receive at least one treatment. Outcomes will be compared to the non-treated side.
OBJECTIVES	The objective of this clinical study is to evaluate the safety and performance of fractional RF for the treatment of surgical scars following breast augmentation, abdominoplasty or face lift.

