7.3.2 ENROLLMENT/BASELINE

Enrollment/Baseline Visit (Visit 2, Day 0)

Once a subject has been confirmed that they continue to meet inclusion/exclusion criteria, they will receive a unique identifying number that will be composed of a two-digit site number and a two-digit subject number in sequence. This unique identifier will be used throughout the entire study and will be entered in the subject's case report form (CRF). The investigator will confirm that the subject still meets the inclusion/exclusion criteria. Vital signs and demographics will be collected and a physical exam will be performed. The subject will complete the POSAS.

Photography

Photographs will be taken prior to first treatment and throughout the study according to specified time points detailed in the Schedule of Events Table (section 7.3.7), utilizing standard scientific equipment. Two sets of photographs will be required, one set for the treated side of the body/face and a second set for the untreated side of the body/face.

The photos should be taken in a private room or area of the clinic under controlled conditions, including the distance, angle, background and lighting in order to achieve high-quality sets of photographs. Direct illumination will not be used. The subject should be placed in the same position each time. As each photograph is taken, it should be viewed to ensure that it is in focus and is similar to its baseline counterpart in all technical aspects, including lighting, distance and angle.

For consistency purposes, the same person should ideally take all study photographs, especially per subject. The digital files should follow a consistent standard naming scheme.

Treatment

Subjects will receive treatment as described in section 7.3.1. Only one side of the body/face will be treated. The same side will be treated for the duration of the study. Only half of a scar will be treated

and remaining half will serve as the control. Following treatment, the investigator will examine the treated area and report immediate and short term response. Subjects will complete the 10 cm discomfort/pain VAS immediately after treatment. A new disposal tip will be used for each patient treatment.

Treatment procedure should include positioning of the patient in a manner that enables comfortable access to the treated anatomical site.

Assessment

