10.2 STATISTICAL HYPOTHESES

The null and alternative hypotheses for the study's primary, key secondary and safety endpoints are;

- Primary Performance Endpoint:
 - **Null Hypothesis ($H_0: \mu_d = \mu_{post} - \mu_{pre} = 0$)** – There is no improvement of surgical scars at 3 months post-treatment review compared to baseline.
Alternative Hypothesis ($H_a: \mu_d = \mu_{post} - \mu_{pre} \neq 0$) – There is improvement of surgical scars at 3 months post-treatment review compared to baseline. The improvement of surgical scars will be defined by General Aesthetic Improvement Scale (GAIS) and Manchester Scar Scale (MSS) scores evaluated by independent blinded reviewer. Expected mean improvement difference is not less than one (1) GAIS and MSS score higher than baseline.
 - **Null Hypothesis ($H_0: \mu_d = \mu_{post} - \mu_{pre} = 0$)** – There is no improvement of surgical scars at 10 months post-treatment review compared to baseline.

Alternative Hypothesis ($H_a: \mu_d = \mu_{post} - \mu_{pre} \neq 0$) – There is improvement of surgical scars at 10 months post-treatment review compared to baseline. The improvement of surgical scars will be defined using General Aesthetic Improvement Scale (GAIS) and Manchester Scar Scale (MSS) scores evaluated by independent blinded reviewer. Expected mean improvement difference is not less than one (1) GAIS and MSS score higher than baseline.

- Secondary Performance Endpoint(s):
 - **Null Hypothesis ($H_0: \mu_d = \mu_{post} - \mu_{pre} = 0$)** – There is no improvement of surgical scars at 1 and 2 months post-treatment review compared to baseline.
Alternative Hypothesis ($H_a: \mu_d = \mu_{post} - \mu_{pre} \neq 0$) – There is improvement of surgical scars at 1 and 2 months post-treatment review compared to baseline. The improvement of surgical scars will be defined using General Aesthetic Improvement Scale (GAIS) and Manchester Scar Scale scores evaluated by independent blinded reviewer.
 - **Null Hypothesis ($H_0: \mu_d = \mu_{post} - \mu_{pre} = 0$)** – There is no improvement of surgical scars at 3 and 10 months post-treatment review compared to baseline.
Alternative Hypothesis ($H_a: \mu_d = \mu_{post} - \mu_{pre} \neq 0$) – There is improvement of surgical scars at 3 and 10 months post-treatment review compared to baseline. The improvement of surgical scars will be defined using Patient and Observer Scar Assessment Scale (POSAS) scores evaluated by independent blinded reviewer.

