10.4 DESCRIPTION OF STATISTICAL METHODS

10.4.1 GENERAL APPROACH

All summary tables for quantitative parameters will display mean, standard deviation, median, range (minimum and maximum), percentages as well as number of missing data (if relevant). All summary tables for qualitative parameters will display counts, percentages and number of missing data if relevant. Baseline data are defined as the last measurement performed before the first treatment on Visit 2.

All statistical tests will be two-sided. The level of statistical significance for effectiveness analyses is 5% ($\alpha = 0.05$) for all tests of differences. Where appropriate, Paired t-test and/or Wilcoxon Signed-Ranks Test for Matched Pairs will be used to compare the evaluations at the baseline and post treatment sessions. This test will enable us to accept or reject the null hypotheses. Rejection of null hypotheses will establish that:

- The two-sided 95% confidence interval for the difference between the means excludes zero.
- The two means are statistically significantly different at the 5% level ($P < 0.05$) two-sided.

Upon rejection of null hypotheses, further statistical test tools such as Confidence Interval and/or t-test will be used to determine the performance of Venus Viva™ fractional RF System in the treatment of surgical scars following breast augmentation, abdominoplasty or face lift.

In order to accommodate imbalances of some baseline General Aesthetic Improvement Scale (GAIS) and Manchester Scar Scale (MSS) scores, covariate adjustment analysis may be performed in SAP to estimate adjusted treatment effects for the primary endpoint analysis.

The assumption for the statistical test is that the paired differences of baseline and post treatment data are normally distributed.

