10.4.2 ANALYSIS OF THE PRIMARY PERFORMANCE ENDPOINT(S)

The following will be considered for the analysis primary performance endpoint:

Summary table for differences of baseline, 3-month and 10-month post treatment General Aesthetic Improvement Scale (GAIS) and Manchester Scar Scale (MSS) scores will be displayed as mean difference, standard deviation and standard error. The General Aesthetic Improvement Scale (GAIS) scores is a 5-point scale improvement assessment chart while Manchester Scar Scale (MSS) is two scales whose scores are combined - an overall VAS and seven scar parameters.

Bar, pie charts or graphs indicating scores will also be used to analyse performance, where applicable.

All statistical tests will be two-sided. The level of statistical significance for effectiveness analyses is 5% ($\alpha = 0.05$) for all tests of differences. Where appropriate, Paired t-test and/or Wilcoxon Signed-Ranks Test for Matched Pairs will be used to compare the evaluations of General Aesthetic Improvement Scale (GAIS) scores and Manchester Scar Scale (MSS) scores at 3 and 10 months against baseline. Analysis of Covariance (ANCOVA) may also be used where appropriate.

The Paired t-test and/or Wilcoxon Signed-Ranks Test for Matched Pairs will enable us to accept or reject the null hypotheses. Rejection of null hypotheses will establish that:

- The two-sided 95% confidence interval for the difference between the means excludes zero.
- The two means are statistically significantly different at the 5% level ($P < 0.05$) two-sided.

Upon rejection of null hypotheses, further statistical test tools such as Confidence Interval and/or t-test will be used to test expected primary performance endpoint; that is alternative hypothesis that $H_a \geq 1$. This will be used to determine if the study meets the primary performance endpoint.

General Aesthetic Improvement Scale (GAIS) scores and Manchester Scar Scale (MSS) scores of all subjects who received at least one treatment of Venus Viva™ system for the treatment of surgical scars following breast augmentation, abdominoplasty or face lift and for whom at least one valid post-baseline GAIS and MSS assessment were obtained will be analysed for the primary endpoint. Multiple imputation method or modelling of available data may be used for missing data as appropriate.

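### The untreated half is the stated control, but the performance hypotheses, tests and sample size use change from baseline, so natural scar change is counted as device effect

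*Combined protocol and SAP*

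**What the plan says.** The design is a within-subject comparison. The Protocol Summary says: "Outcomes will be compared to the non-treated side". Section 7.3.2 treats half of the scar and says the "remaining half will serve as the control". The same section, under Photography, says "Two sets of photographs will be required", one for the treated and one for the untreated side.

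The statistical sections use a different comparison.

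- **10.2:** each performance hypothesis is written as μ_post − μ_pre = 0. The first primary null reads: "There is no improvement of surgical scars at 3 months post-treatment review compared to baseline".
- **10.4.1:** the paired t-test and/or Wilcoxon signed-rank test "will be used to compare the evaluations at the baseline and post treatment sessions", and the normality assumption is stated for those same baseline-to-post differences.
- **10.4.2:** the primary tests compare "GAIS) scores and Manchester Scar Scale (MSS) scores at 3 and 10 months against baseline". After rejection, a second step tests Ha ≥ 1. Of that step the plan says: "This will be used to determine if the study meets the primary performance endpoint".
- **10.5:** the sample size rests on the 3-month GAIS change from baseline, with mean 1.0 and SD 1.0.

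No hypothesis, test or model in section 10 names the untreated side.

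**The concern.** A change from baseline on the treated side is the sum of any device effect and whatever the scar would have done untreated. Section 5.2 admits scars from four weeks after surgery, with no upper limit on scar age. The primary readings come 3 and 10 months after the last treatment. A scar that is still maturing can therefore change over the study for reasons unrelated to the device, as can the reviewer's scoring. The untreated half is there to remove these influences, and the planned primary analysis does not use it.

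At stake is what a positive trial would mean. Rejecting the null, or passing the Ha ≥ 1 step, would support improvement since entry. It would not support attributing that improvement to fractional RF.

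**Working it through.** **1. Reproduce the plan's sample size (10.5).** Matched-pairs formula: n = [σ_d (z₁₋α/₂ + z₁₋β) / μ_d]².

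- Inputs from 10.5: σ_d = 1.0 (GAIS range 4 ÷ 4), μ_d = 1.0, two-sided α = 0.05, power 0.90.
- n = (1.960 + 1.282)² = 10.51, rounded to 11. With 30% added, 11 × 1.3 = 14.3, rounded to 15. Both match the plan.
- The table prints 0.84 as the z-value for 90% power. That would give (1.96 + 0.84)² = 7.84, or 8, so the stated 10.51 used 1.28.

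The pair behind the 11 is post and pre on one side. No untreated-side quantity enters.

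**2. Effect of natural change on the first step.** Assumptions, not in the documents: no device effect, untreated scars improve by m GAIS points, SD of change 1.0, n = 11. The probability of rejecting in the favourable direction is the upper tail of a noncentral t with 10 degrees of freedom and noncentrality m√11, beyond the 97.5% critical value.

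| m | Favourable rejection (nominal 2.5%) |
|---|---|
| 0.25 | 11% |
| 0.5 | 32% |
| 1.0 | 85% |

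**3. First step plus the Ha ≥ 1 step.** Section 10.4.2 does not say how Ha ≥ 1 is decided. Three readings were simulated under the same assumptions, with 2,000,000 trials per shift:

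| Reading of the second step | m = 0.25 | m = 0.5 | m = 1.0 |
|---|---|---|---|
| Observed mean at least 1 | 0.6% | 5% | 50% |
| Lower 95% limit at least 1 | about 0% | 0.02–0.03% | 2.5% |
| Upper 95% limit at least 1 | 10% | 30% | 84% |

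On every reading the estimate is shifted by m, which is 25%, 50% or 100% of the 1-point margin.

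**4. Sample size for the side contrast.** Assume SD 1.0 per side and between-side correlation ρ. The SD of the side difference is √[2(1 − ρ)], so n = 10.51 × 2(1 − ρ) / gap².

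| Gap | ρ | Evaluable per cohort | With 30% added |
|---|---|---|---|
| 1.0 | 0.5 | 11 | 15 |
| 1.0 | 0.3 | 15 | 20 |
| 1.0 | 0.1 | 19 | 25 |
| 1.0 | 0 | 22 | 29 |
| 0.5 | 0.5 | 43 | 56 |
| 0.5 | 0 | 85 | 111 |

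These figures use the sponsor's normal formula. With 11 evaluable, an SD of the difference of 1.0 and a gap of 1.0, the exact paired t-test has 84.8% power; 90% needs 13.

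**The case against.** The control is omitted from section 10, not ruled out. The Protocol Summary states the side comparison. Sections 10.4.1 and 10.4.2 allow covariate adjustment or ANCOVA, and 10.1 allows a revised SAP before database lock. The endpoints speak of improvement, and the objective does not claim superiority over no treatment. This does not answer the point. The summary sentence gives no hypothesis, test or success rule. The adjustments are optional, 10.4.1 ties its adjustment to imbalance in baseline scores, and neither names side. A later SAP could repair the plan, but the present one has to be judged as written.

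Four cautions stand.

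- The rates rest on assumed natural change. The 85% requires untreated scars to improve by the sponsor's whole expected effect.
- The 11%, 32% and 85% are first-step rates, not rates of declaring success. If the lower limit must reach 1, false success does not exceed 2.5% over the range shown.
- Cohorts appear only in 10.5, while 10.3 and 10.4.2 analyse all subjects. With 33 pooled subjects (3 × 11), first-step rates for shifts of 0.25 and 0.5 rise to about 29% and 80%. The joint rates on the observed-mean reading fall to about 0.001% and 0.2%.
- The schedule in 7.3.7 has one row per scale. This does not prove that sides will go unscored; it shows only that per-side scoring is not written down.

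None of these restores the missing comparison or removes the bias in the estimate.

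**Conclusion.** The concern holds and must be fixed. The protocol promises treated against untreated, and section 10 tests treated against its own baseline. This follows from the text and needs no assumption. As written, the primary result contains all change not caused by the device, and a positive finding cannot be attributed to fractional RF.

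How often this would mislead cannot be fixed from the documents, so the rates above are illustrative. The firmer conclusion is bias: the estimate of device effect is off by exactly the natural change, whatever the second-step rule.

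**What to change.** - **10.2, 10.4.1–10.4.3 and 10.5:** make the within-subject treated-minus-untreated difference at 3 and 10 months the primary contrast. Keep change from baseline as descriptive.
- **Ha ≥ 1 step:** apply it to the side difference with one stated decision rule, or drop it.
- **MSS and reviewer POSAS:** test the side difference adjusted for the baseline side difference.
- **GAIS:** compare the two sides' ratings directly by signed-rank test, without subtracting a baseline score. Section 10.4.2 says GAIS "scores is a 5-point scale improvement assessment chart", so the baseline GAIS scheduled in 7.3.7 and summarised in 10.4.6 has no clear meaning.
- **Scoring:** state that the blinded reviewer scores each side's photographs. Analyse subject POSAS by side only if it is collected by side.
- **10.6.1:** state how the treated side is chosen. No rule is given, and the side contrast depends on it.
- **7.3.2–7.3.4:** reconcile side of body or face with half of a scar, so that the control unit is unique. Align the Visit 8–11 photograph wording, which mentions only the treated area and cites 7.3.1, with the two-set requirement in 7.3.2.
- **10.5:** give and justify the SD and correlation for a side difference.

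Most of the cost is wording plus a small form change, because both sides are already photographed. The sample size may also be affected. For a 1-point gap and SD 1.0 per side, the planned 15 per cohort suffices by the sponsor's formula only at ρ of about 0.5 or more. The enrolment caps (25 face lift; 25 each for the other two if the 50 splits evenly) suffice at about 0.1 or more. A 0.5-point gap needs 43 to 85 evaluable per cohort for ρ from 0.5 to 0, beyond the caps, so the stated power may be less favourable.

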10.5 SAMPLE SIZE

One of the primary performance endpoints outcome measures was used to calculate the study sample size.

Sample size calculation using the subject's improvement of surgical scars at 3 months post-treatment as evaluated by independent blinded reviewer using the General Aesthetic Improvement Scale (GAIS);

- Null and alternate hypotheses:
 - **Null Hypothesis ($H_0: \mu_d = \mu_{post} - \mu_{pre} = 0$)** – There is no improvement of surgical scars at 3 months post-treatment review compared to baseline.
 - **Alternative Hypothesis ($H_a: \mu_d = \mu_{post} - \mu_{pre} \neq 0$)** – There is improvement of surgical scars at 3 months post-treatment review compared to baseline. The improvement of surgical scars will be defined by General Aesthetic Improvement Scale (GAIS) scores evaluated by independent blinded reviewer. Expected mean improvement difference is not less than one (1) GAIS score higher than baseline.
- In view of the nature of this study in regard to treatment period of 3 months and up to 10 months follow-up, we make provision for 30% study drop out, withdrawal or loss to follow-up.
- Due to the natures of 3 types of surgical scars that will be treated in this clinical study, the study will be viewed as 3 groups of cohort studies;
 - breast augmentation cohort group
 - abdominoplasty cohort group
 - face lift cohort groupThe study's sample size calculation below is number of subjects required for each group the makes up the study
- 2-Tailed Sample Size calculation formula for Matched Samples was used in the table below:

(1- β), Power	0.9
α , Level of Significance	0.05
μ_d , mean difference; this is the expected improvement (difference) to treatment assessed by GAIS scores under H_a	1.0
σ_d , Standard Deviation of the difference scores (GAIS range $\div 4$) = [4 \div 4]	1.0
ES, Effect Size $[(\mu_d/\sigma_d)]$	1.0
$Z_{1-\alpha/2}$	1.96
$Z_{1-\beta}$, (for 90%)	0.84
Estimated Sample Size	10.51 \approx 11
Estimated Sample Size + 30% drop out	14.30 \approx 15

Conclusion: The estimated sample size for each cohort group obtained from the primary performance endpoint outcome measure calculation plus 30% drop out provision that will be used for this study is 15.

The study will enroll up to 50 female subjects requesting treatment of surgical scars following breast augmentation or abdominoplasty and up to 25 male and female subjects requesting treatment of surgical scars following face lift surgery.

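### The 90% power is for rejecting zero, but the primary endpoint is decided by a later, undefined test of a mean of at least 1, which is exactly the planning mean

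*Combined protocol and SAP*

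**What the plan says.** Section 10.4.2 describes two steps for GAIS and MSS at 3 and 10 months. The first is a paired t-test and/or Wilcoxon signed-rank test of the change from baseline against zero, at the 5% level; "All statistical tests will be two-sided". If zero is rejected, "further statistical test tools such as Confidence Interval and/or t-test will be used to test expected primary performance endpoint", written as an alternative of at least 1. The section then adds: "This will be used to determine if the study meets the primary performance endpoint". The second step therefore decides the endpoint.

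Section 10.5 sizes the study on GAIS at 3 months. The null is a zero mean difference, and "2-Tailed Sample Size calculation formula for Matched Samples was used in the table below". The inputs are power 0.9, alpha 0.05, mean difference 1.0 and SD of differences 1.0 (GAIS range 4 divided by 4). The results are 10.51, rounded to 11, and 15 after the dropout allowance. The figure applies to each of the three scar cohorts: "sample size calculation below is number of subjects required for each group". The same section states: "Expected mean improvement difference is not less than one (1) GAIS score higher than baseline". Section 10.2 repeats that expectation for both GAIS and MSS at both time points. No section gives power for the second step.

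**The concern.** Two problems compound each other. First, the success rule is not determinate. A confidence interval and/or a t-test can be set against the value 1 in several ways, and 10.4.2 does not choose one or say whether the rule applies per cohort or pooled. Second, the power statement belongs to a different question. The 90% is the chance of rejecting zero when the true mean is 1.0. The endpoint is decided by comparing the mean with 1.0, and the plan assumes the truth is exactly there. If the second step is a significance test above 1, a true mean of 1.0 is its null boundary, so it passes only at its type I error rate and no increase in sample size helps.

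A reader would take 90% as the chance of meeting the primary endpoint. An open rule could also be settled once results are known, and section 10.6.2 says the biostatistician is not blinded.

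**Working it through.** **Inputs (section 10.5 unless noted).** Two-sided alpha 0.05; power 0.90; mean difference 1.0; SD of differences 1.0; dropout 30%; n per cohort. Section 10.4.1 assumes that paired differences are normally distributed.

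**The plan's own figure.** n = ((z₀.₉₇₅ + z₀.₉₀) × SD / mean)² = (1.96 + 1.2816)² = 10.51, rounded to 11. This reproduces. The table prints 0.84 for the power term, which is the 80% value and would give (1.96 + 0.84)² = 7.84. The calculation therefore used 1.28, and the printed 0.84 does not affect n.

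**Dropout.** The plan takes 11 × 1.3 = 14.3, rounded to 15. Keeping 11 evaluable after 30% loss needs 11 / 0.7 = 15.7, rounded to 16. With 15 enrolled, 15 × 0.7 = 10.5, so 10 to 11 remain.

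**Step 1 only: power against zero by paired t-test** (noncentral t, effect size 1.0, two-sided 5%):

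| n evaluable | Power |
|---|---|
| 10 | 80.3% |
| 11 | 84.8% |
| 12 | 88.3% |
| 13 | 91.1% |
| 15 | 94.9% |
| 17 | 97.2% |

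The formula in 10.5 is a normal approximation, so a paired t-test with 11 subjects falls short of 90% even for this step.

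**Both steps: true mean 1.0, SD 1.0, normal differences** (simulation, 2,000,000 runs per n):

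| Reading of step 2 | n=10 | n=11 | n=13 | n=15 | n=52 |
|---|---|---|---|---|---|
| Lower limit of two-sided 95% CI above 1 | 2.5% | 2.5% | 2.5% | 2.5% | 2.5% |
| One-sided 5% test above 1 | 5.0% | 5.0% | 5.0% | 5.0% | 5.0% |
| Observed mean at least 1 | 49.7% | 49.9% | 49.9% | 50.0% | 50.0% |
| Interval not wholly below 1 | 79.8% | 84.1% | 90.2% | 93.7% | 97.5% |

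The first two rows do not move with n because the true mean is on the boundary: t = (mean − 1) / (SD/√n) then has a central t distribution and exceeds its critical value with probability 0.025 or 0.05. The n=52 column pools all 75 subjects less 30% (75 × 0.7 = 52.5).

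**Above the planning value.** The documents give no expected mean above 1, so 1.5 is an assumption for illustration. Under the strict two-sided reading the chance of success is then 29.3% at n=10, 32.3% at n=11, 43.8% at n=15, 49.1% at n=17 and 94.3% at n=52. For 90% on that reading the true mean would have to be about 2.09 at n=11, 1.90 at n=15 or 1.46 at n=52.

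**The case against.** The strongest reply is that 2.5% is the harshest reading. Section 10.4.2 writes the alternative as at least 1, which includes 1, and sections 10.2 and 10.5 call it an expected improvement. The 5% figure also needs a one-sided test, although the plan makes all tests two-sided. This stands as a limit on those two figures: each is one scenario. It does not rescue the plan, because 10.4.2 says the step will be tested and will decide the endpoint, and the gap between readings is itself the defect.

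Section 10.1 says a revised SAP would be issued before database lock and unblinding. That gives some protection, but it is conditional on a revision and does not supply the rule.

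Ten to eleven evaluable subjects is the full-loss case. The caps allow more: 25 in a cohort less 30% leaves 17 (25 × 0.7 = 17.5), with 97% power against zero. For breast and abdomen this assumes the 50 split evenly. The 30% also covers follow-up to 10 months, while the powered outcome is at 3 months. This is a fair point about the first step. It does not alter the strict or point-estimate readings at a true mean of 1.0.

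GAIS is a 5-point scale, so differences are integers. Under assumed integer distributions with mean 1 and SD about 1, the point-estimate rule passes about 54 to 56% of the time at n=10 to 11, because ties at exactly 1 count. If differences are confined to 0 to 4, power against zero at n=11 is about 93%, and the most lenient reading reaches about 90 to 91%. The exact figures therefore depend on the plan's normality assumption. The ordering and the wide spread do not.

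The misprinted 0.84 and the difference between 15 and 16 are minor and carry no weight in the main conclusion.

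**Conclusion.** The concern holds. The stated 90% is power to reject zero, whereas the endpoint is declared met by a further comparison with 1, which has no defined rule and no stated power. At the planning mean and SD, with 10 to 11 evaluable per cohort, the choice of reading alone moves the chance of success from 2.5% to 80–84%, and under the plan's own normality assumption no reading reaches 90%. If step 2 is a significance test above 1, the chance stays at 2.5% (two-sided) or 5% (one-sided) at any sample size while the true mean is 1.0.

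These figures rest on mean 1.0, SD 1.0 and normal differences, for GAIS at one time point in one cohort. They do not cover MSS, for which the plan gives no planning inputs, or a requirement to succeed on both scales or at both times.

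**What to change.** In 10.4.2, with matching wording in 10.2, the sponsor should choose one of two routes.

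1. Keep the 1-point step. State exactly how it is judged (which confidence limit or test, one- or two-sided, per cohort or pooled), and give its power at a mean of 1 and at the mean the sponsor expects.
2. Make the test against zero the success criterion, and report the mean difference with its 95% CI beside the 1-point reference.

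In 10.5:

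- Say that the 90% refers to the test against zero only.
- Replace 0.84 with 1.28, and inflate for dropout by n / (1 − 0.30).
- Restate power by paired t-test as about 80–85% for 15 enrolled per cohort after the full 30% loss, and about 95% with no loss.
- If 90% by paired t-test is wanted after that loss, 13 evaluable are needed per cohort: 13 / 0.7 = 18.6, so 19 enrolled. That fits the caps (2 × 19 = 38 of 50 for breast and abdomen; 19 of 25 for face).

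The protocol summary compares outcomes with the untreated side, while 10.2 and 10.5 compare with baseline. If that comparison changes, the power figures must be redone.

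The cost is revised wording and figures within the 75-subject cap, plus the ethics approval that section 13.2 requires for any amendment. Route 1 may show a much lower power; route 2 reduces the 1-point claim to a descriptive one.
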